7.6.6.2. Regulatory Reporting Requirements for SAEs

Prompt notification by the investigator to GSK of SAEs and non-serious AEs related to study treatment (even for non-interventional post-marketing studies) is essential so that legal obligations and ethical responsibilities towards the safety of subjects and the safety of a product under clinical investigation are met.

GSK has a legal responsibility to notify both the local regulatory authority and other regulatory agencies about the safety of a product under clinical investigation. GSK will comply with country specific regulatory requirements relating to safety reporting to the regulatory authority, Institutional Review Board (IRB)/Independent Ethics Committee (IEC) and investigators.

Investigator safety reports are prepared for suspected unexpected serious adverse reactions according to local regulatory requirements and GSK policy and are forwarded to investigators as necessary.

An investigator who receives an investigator safety report describing a SAE(s) or other specific safety information (*e.g.*, summary or listing of SAEs) from GSK will file it with the IB (GSK Document Number 2014N190256_01and will notify the IRB/IEC, if appropriate according to local requirements.

7.6.7. Pregnancy

Any pregnancy (participating females and female partners of participating males) that occurs during study participation must be reported using a clinical trial pregnancy form. To ensure subject safety, each pregnancy must be reported to GSK within 2 weeks of learning of its occurrence and should follow the procedures outlined in Appendix 12.5.

7.6.8. Physical Exams

- A complete physical examination at screening will include, at a minimum, assessment of the CV, Respiratory, Gastrointestinal and Neurological systems. Height and weight will also be measured and recorded.
- A brief physical examination at subsequent visits will include, at a minimum assessments of the skin, lungs, CV system, and abdomen (liver and spleen).
- Investigators should pay special attention to clinical signs related to previous serious illnesses.

7.6.9. Vital Signs

- Vital signs will be performed prior to dosing with GSK3196165.
- Vital signs will be collected as indicated in the Time and Event Table (Section 7.1).
- Vital signs will be measured in semi-supine position after 5 minutes rest and will include temperature, systolic and diastolic blood pressure, pulse rate, and respiratory rate.
- A single set of values will be collected and recorded in the source documentation and eCRF.

7.6.10. Electrocardiogram

See Section 5.2 regarding QTc exclusion criteria.

Single 12-lead ECGs will be obtained (before dosing, vital signs measurements and blood samples taken) at the time points after Day 1 presented in the Time and Events Table (Section 7.1) during the study using an ECG machine that automatically calculates the heart rate and measures PR, QRS, QT, and QTc intervals. The ECG may be repeated in triplicate if the recorded QTcF value is out of range. The QTc should then be based on averaged QTc values of the triplicate ECGs obtained over a brief recording period (*e.g.*, 5-10 minutes). Refer to Section 5.4.2 for QTc withdrawal criteria and additional QTc readings that may be necessary.

7.6.11. Clinical Safety Laboratory Assessments

All protocol required laboratory assessments, as defined in Section 7.1, must be conducted in accordance with the Laboratory Manual, and Protocol Time and Events Schedule (Section 7.1). Laboratory requisition forms must be completed and samples must be clearly labelled with the subject number, protocol number, site/center number, and visit date. Details for the preparation and shipment of samples will be provided by the laboratory and are detailed in the Central Laboratory Manual. Reference ranges for all safety parameters will be provided to the site by the laboratory responsible for the assessments.

If additional non-protocol specified laboratory assessments are performed at the institution's local laboratory and result in a change in subject management or are considered clinically significant by the investigator (*e.g.*, SAE or AE or dose modification) the results must be recorded in the eCRF.

Refer to the central laboratory manual for appropriate processing and handling of samples to avoid duplicate and/or additional blood draws.

All study-required laboratory assessments will be performed by a central laboratory, apart from:

• ESR

The results of any locally performed test must be entered into the eCRF.

NOTE: Local laboratory results are only required in the event that the central laboratory results are not available in time for either a treatment and/or response evaluation to be performed. If a local sample is required it is important that the sample for central analysis is obtained at the same time. Additionally if the local laboratory results are used to make either a treatment or response evaluation, the results must be entered into the eCRF.

Hematology, clinical chemistry, urinalysis and additional parameters to be tested are listed in Table 2.

Table 2 Protocol Required Safety Laboratory Assessments

Hematology	Biochemistry	Urinalysis
Hemoglobin	Sodium	Urine dipstick
Hematocrit	Potassium	Glucose
Mean cell volume (MCV)	Calcium	Protein
Mean corpuscular hemoglobin (MCH)	Phosphate	
Mean corpuscular hemoglobin concentration	Urea	Microscopy of
(MCHC)	Creatinine	urine sediment for
Erythrocyte count	Creatinine clearance	erythrocytes,
Reticulocyte count	(calculated)	leukocytes and
Leukocyte count	AST	casts if urine
Leukocyte differential count	ALT	dipstick abnormal
neutrophils	y-glutamyl transpeptidase	-

Hematology	Biochemistry	Urinalysis
eosinophils	(GGT)	Urine pregnancy
basophils	LDH	test
monocytes	Alkaline phosphatase (AP)	
lymphocytes	Bilirubin (total)	
Platelets	Creatine Phosphokinase	
Activated partial thromboplastin time (aPTT)	(CPK)	
Prothrombin Time (PT)	Total protein	
International Normalized Ratio (INR)	Albumin	
Fibrinogen	Albumin/globulin ratio	
ESR*	Serum Glucose	
	CRP	
	Cholesterol**	
	Triglycerides**	
	HDL**	
	LDL**	

*Measured locally

**Fasting tests

All laboratory tests with values that are considered clinically-significantly abnormal during participation in the study or within 12 weeks after the last dose of study treatment should be repeated until the values return to normal or baseline. If such values do not return to normal within a period judged reasonable by the investigator, the etiology should be identified and the sponsor notified.

Serum will be collected at baseline and throughout the study to measure potential biomarkers of lung damage such as SP-D, KL-6, LDH, and cholestenoic acid (see Section 7.3.2). Baseline measurement of GM-CSF autoantibodies will be measured.

7.6.12. Pulmonary Assessments

Pulmonary assessments are a key aspect of the safety monitoring in this study.

The following pulmonary assessments will be performed at the time points presented in the Time and Events Table (Section 7.1).

- Chest X-ray.
- Cough.
- Borg dyspnea questionnaire.
- Lung auscultation.
- Pulse oximetry.
- PFTs spirometry (FEV1, FVC), gas transfer (D_{LCO}).

PFTs should be performed according to 2005 ATS/ERS recommendations for lung function testing [MacIntyre, 2005; Miller, 2005a; Miller, 2005b]. Spirometry should be

performed prior to D_{LCO} testing. The standards for acceptable testing sessions are described further in the Pulmonary Safety Guidance document in the SRM.

In the event of any new or clinically significant pulmonary abnormalities that may develop during the study (*e.g.*, increased shortness of breath/dyspnea, or unexplained and persistent coughing; or >15% relative decrease in D_{LCO} from baseline), it is recommended that the subject be referred to a pulmonologist for further assessment. The study treatment should be suspended until the symptoms or signs that caused referral have resolved and/or the underlying diagnosis has been determined and clinically significant events have been excluded by the pulmonologist. Suggested pulmonary assessment/management algorithms are provided in a separate Pulmonary Safety Guidance Document in the SRM.

Additional pulmonary imaging (HRCT) or other tests may be performed on a subject during the study to investigate pulmonary abnormalities, and the SRT may request copies of any reports or images for central review.

7.7. Pharmacokinetics

Details of PK blood sample collection, processing, storage and shipping procedures are provided in the central laboratory manual.

7.7.1. Blood Sample Collection

Blood samples for PK analysis of GSK3196165 will be collected at the time points indicated in Section 7.1, Time and Events Table. The actual date and time of each blood sample collection will be recorded. The timing of PK samples may be altered and/or PK samples may be obtained at additional time points to ensure thorough PK monitoring.

Details of PK blood sample collection, processing, storage and shipping procedures are provided in the central laboratory manual.

7.7.2. Sample Analysis

Sample analysis will be performed under the control of GSK. Concentrations of GSK3196165 will be determined in serum samples using the currently approved bioanalytical methodology. Raw data will be archived at the bioanalytical site (detailed in the SRM).

7.8. Immunogenicity

GSK3196165 is a humanized monoclonal antibody that will be delivered by the subcutaneous route and is targeted to bind and neutralize a soluble target, and for these reasons, is considered to be a relatively low risk of inducing adverse immune responses [FDA, 2014].

Serum samples will be collected and tested for presence of antibodies that bind to GSK3196165 anti-drug antibodies (ADAs). Serum samples for testing anti-GSK3196165 antibodies will be collected as described in the Time and Events schedule (Section 7.1). The actual date and time of each blood sample collection will be recorded. Details of blood sample collection (including volume to be collected), processing, storage and shipping procedures are provided in the Central Laboratory Manual.

The timing and number of planned immunogenicity samples may be altered during the course of the study, based on newly-available data to ensure appropriate safety monitoring. In the event of a hypersensitivity reaction that is either 1) clinically-significant in the opinion of the investigator, or 2) leads to the subject withdrawing from the study, blood samples should be taken from the subject for immunogenicity testing, at the time of the event and again 12 weeks after. For subjects who prematurely withdraw from the study, immunogenicity testing will occur at withdrawal and at follow-up 12 weeks after last dose.

Serum will be tested for the presence of anti-GSK3196165 antibodies using the currently approved analytical methodology using a tiered testing schema: screening, confirmation and titration steps. The presence of treatment emergent ADA will be determined using a GSK3196165 bridging style ADA assay with a bio-analytically determined cut point determined during assay validation. Samples taken after dosing with GSK3196165 that have a value at or above the cut-point will be considered treatment-emergent ADA-positive. These ADA positive samples will be further evaluated in a confirmatory assay, and confirmed positive samples will be further characterized by assessment of titer. Results of anti-GSK3196165 antibody testing will be reported at the end of the study and will include incidence and titer. The presence or absence of antibodies to GSK3196165 in dosed subjects will be analyzed, then summarized descriptively and/or graphically presented.

7.9. Magnetic Resonance Imaging

Each subject's most affected wrist (corresponding to the affected hand which is determined and documented at screening) will be imaged by MRI at Screening, Week 4, Week 12 and Week 22 (see Section 7.1). If a scanning failure occurs at any visit, if feasible a rescan is allowed within 7 days after the failed scan after consultation and agreement with the Medical Monitor. There will be a minimum of 24 hours between scans where gadolinium (Gd) contrast is used. The MRI will be used in order to non-invasively quantify the degree of inflammation and structural changes within the target joint.

Each MRI total scan time should not exceed 1 hour. For each subject, MRIs must be performed on the same scanner and using the same type of chelated Gd contrast agent as was used at screening. If scanning cannot occur on the same scanner within the visit time window due to hardware failure, an alternate scanner may be used or the time window may be extended by 3 days only after consultation and agreement with the Medical Monitor.

On attendance at the MRI department, subjects will be placed in the scanner and will be prepared for intravenous contrast agent administration. The scanning protocol will include routine localizers, T1 measurement sequences, DCE-MRI acquisition, and acquisitions required for OMERACT RAMRIS and RAMRIQ scoring. Additional exploratory MRI endpoints, as detailed in the Imaging Acquisition Manual, may also be acquired for exploratory purposes.

Details of scanning site training procedures, acceptable Gd contrast agents, and scanning protocols will be provided in a dedicated Imaging Acquisition Manual.

All MRI scans will be available at site, and may be reported at the site by a radiologist (non-anonymized) for clinical abnormalities per local standard procedures.

7.10. Genetics

Information regarding genetic research is included in Appendix 12.6.

7.11. Value Evidence and Outcomes

Planned timepoints for all health outcomes assessments are presented in the Time and Events Table (Section 7.1), and further details of all assessments are provided in the SRM.

7.11.1. Health Assessment Questionnaire – Disability Index (HAQ-DI)

The functional status of the subject will be assessed by means of the HAQ-DI. This 20-question instrument assesses the degree of difficulty a person has in accomplishing tasks in eight functional areas [Fries, 1980]:

• Dressing and grooming, arising, eating, walking, hygiene, reach, grip, and common daily activities.

7.11.2. Rheumatoid Arthritis Symptoms and Impact Diary PRO

Symptoms associated with RA will be assessed using a novel RA Symptom and Impact Diary, as per the Time and Events Schedule (Section 7.1).

8. DATA MANAGEMENT

- For this study, subject data will be entered into GSK defined CRFs, transmitted electronically to GSK or designee and combined with data provided from other sources in a validated data system.
- Management of clinical data will be performed in accordance with applicable GSK standards and data cleaning procedures to ensure the integrity of the data, *e.g.*, removing errors and inconsistencies in the data.
- Adverse events and concomitant medications terms will be coded using MedDRA (Medical Dictionary for Regulatory Activities) and an internal validated medication dictionary, GSKDrug.

• eCRFs (including queries and audit trails) will be retained by GSK, and copies will be sent to the investigator to maintain as the investigator copy. Subject initials will not be collected or transmitted to GSK according to GSK policy.

9. STATISTICAL CONSIDERATIONS AND DATA ANALYSES

9.1. Hypotheses

No formal hypotheses are to be tested. Differences between the treatment groups for the MRI synovitis data will be assessed by deriving the 95% credible interval. The analysis will be performed in a Bayesian framework, making use of historical data on the placebo arm where appropriate. The posterior distribution of the treatment difference will be computed, conditional on the observed data and the assumed prior distribution and the 95% credible interval will be derived from the posterior distribution.

For all other endpoints, differences between the treatment groups will be assessed using 95% confidence intervals (CIs). Historical data may be used where available.

9.2. Sample Size Considerations

The sample size for this study is based on feasibility.

9.2.1. Sample Size Assumptions

For the MRI synovitis data, based on a review of results in the literature, the standard deviation (SD) for both treatment groups is assumed to have a value of 2.5. Based on this value, assuming prior information cannot be used, with 30 subjects on GSK3196165 180 mg and 10 subjects on placebo, aiming for 50% early and 50% established RA subjects, it is estimated that the lower and upper bounds of the 95% CI for the difference would be within 1.8 points of the difference. This is considered the worst case precision and further estimates assuming different weights for the prior distribution on placebo will be assessed to estimate any improvement in the precision of the CI.

9.2.2. Sample Size Sensitivity

Not applicable.

9.2.3. Sample Size Re-estimation or Adjustment

Not applicable.

9.3. Data Analysis Considerations

9.3.1. Analysis Populations

The primary population will be the Intent-to-Treat (ITT) population, defined as all subjects who were randomized to treatment and who received at least one dose of study treatment.

9.3.2. Final Analysis

The final analysis will be conducted when all subjects have completed their last follow up visit.

9.3.3. Interim Analysis

No interim analysis is planned for this study.

9.4. Key Elements of Analysis Plan

Full details of all analyses will be provided in the analysis plan.

For the MRI data, the primary analysis will be a repeated measures Bayesian model for the difference between treatments over each visit. The full details of this approach will be provided in the analysis plan.

The data will be analyzed across all subjects, and may also be presented for each disease duration subgroup (stratification factor).

For other continuous endpoints Bayesian and frequentist methods will be used as appropriate.

In addition, the relationship between the mechanistic / biomarker endpoints and clinical effects (*e.g.*, ACR20 Response) will be graphically presented and analyzed using an appropriate statistical model identifying any trends. The model will determine whether the mechanistic / biomarker effect significantly explains or predicts the effect on the clinical endpoints. This may be conducted through comparing statistical models; incorporating different explanatory terms (*i.e.*, mechanistic / biomarker endpoints) with the 'null' model (no mechanistic / biomarker endpoints); or, if deemed appropriate, multivariate statistical methods may also be applied to determine the relationship between the key endpoints. The consistency in the changes over time between the endpoints will also be assessed.

Full details of all summaries and analyses will be given in the RAP.

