pulmonary alveolar proteinosis (PAP)	lung damage (e.g. , Krebs von den				
pathogenesis.	Lungen-6 [KL-6], serum amyloid A (SAA),				
surfactant protein-D [SP-D], cholestenoic					
	aciu). • GM-CSE auto antibodios				

*Where relevant, comparisons will be made between the early and established RA subject populations.

**ACR20/50/70: 20%/50%/70% improvement in tender and swollen joint counts and 20%/50%/70% improvement in 3 of the 5 ACR-core set measures.

Overall Design

This is a randomized Phase IIa, multi-center, double-blind, placebo-controlled parallel group study to explore the mechanistic evidence that the GM-CSF signaling pathway is active in subjects with RA, and the potential impact of inhibition of this axis by GSK3196165. In addition, the study will assess the potential impact of GSK3196165 on inflammatory structural joint damage in the most affected hand/wrist using MRI.

The randomization will be stratified by early or established disease (see below) and randomization will occur at the baseline visit on Day 1.

Treatment Arms and Duration

- Screening period up to 6 weeks, then 10-week combination dosing with methotrexate (MTX), with a 12-week follow-up visit after the last dose (Week 22).
- GSK3196165 180 mg vs. placebo administered by subcutaneous (SC) injection, given weekly for 5 weeks, then every other week thereafter until Week 10.

Type and Number of Subjects

- Approximately 40 subjects with active RA despite treatment with DMARDs (including conventional or biologic) will be randomized into the study.
- Ideally, 50% of subjects enrolled into the study should have early RA (≤2 years since diagnosis). The actual proportion will be monitored throughout the study and randomization may be altered if the projected final proportion with early RA is less than 30%.
- Subjects will be randomized on a 3:1 basis to GSK3196165 or placebo.
- Randomization will be stratified by early RA (≤2 years since diagnosis) and established RA.

Analysis

All endpoints are exploratory. They will be summarized for the overall population as well as by RA status (early *vs.* established). GSK3196165 treatment effect will be measured by change from baseline. They will be presented by tables and figures. The relationships between endpoints will be graphically explored (and further quantified if permitted by adequate data). Bayesian methods will be used to explore the probabilistic aspect of certain endpoints.

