3. OBJECTIVE AND ENDPOINTS

Primary objectives	Primary endpoints			
The main objectives of this study are to explore the activity of GM-CSF signaling pathway characterized by exploratory biomarkers in subjects with RA, the impact of GSK3196165 therapy, and whether there are any differences in this GM-CSF signaling pathway between subjects with early RA or established RA.	Changes from baseline in exploratory biomarkers.			
Secondary objectives	Secondary endpoints			
To evaluate the safety and tolerability of GSK3196165 in subjects with RA.	 Incidence of adverse events (AEs), serious adverse events (SAEs), adverse events of special interest (AESIs). Immunogenicity (anti drug antibodies [ADAs]). 			
To evaluate the impact of GSK3196165 on inflammatory structural joint damage in the hand/wrist using MRI.	 Change from baseline in synovitis, osteitis and erosion as assessed by Outcome Measures in Rheumatology (OMERACT) rheumatoid arthritis MRI scoring system (RAMRIS) and rheumatoid arthritis MRI quantitative score (RAMRIQ) in the most affected hand/wrist. 			
Exploratory Biomarker Endpoints*				
 Identify/validate markers of downstream sign 	naling of GM-CSF and/or potential novel			
 markers for GSK3196165 activity. Pharmacodynamic biomarkers to assess res not limited to, IL-1β, TNFα, IL-6, IL-8, IL-15, CXCL4, CXCL7, CXCL13, CCL22; and com TCC, C4, C4a, sCD163). Effect of GSK3196165 on target cell populat circulating levels of T, B, natural killer (NK), monocytes, dendritic cells, neutrophils). 	sponse to GSK3196165 (e.g. may include, but IL-23, IL-17A/F; chemokines such as CCL17, plement proteins such as C5a, ratio C3/C3dg, ions (e.g. may include, but not limited to, Th17, T regulatory cells and activated			
 Whole blood ribonucleic acid (RNA) markers free GM-CSF/macrophage signaling and res 	s of engagement (e.g. , serum concentration of sponse to GSK3196165.			
 Whole blood deoxyribonucleic acid (DNA) analysis to explore the relationship between genetic variants in the best and response to CSK2106165 				
 Biomarkers of extracellular matrix (ECM) or not limited to, serum chondrex [YKL-40] also 39], ARGS neoepitope). 	aggrecan degradation (e.g. may include, but called human cartilage glycoprotein 39 [HC gp			
 Biomarkers which may be indicative of RA disease activity (e.g., may include, but not limited to 14-3-3n, ACPA, CRP, RF). 				

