 Pharmacodynamic biomarkers which may be may include, but not limited to, C1M, C2M, C metalloproteinase 3 [MMP-3], 14-3-3η). 	e predictive of response to GSK3196165 (e.g. C3M, CRPM, VICM, MRP8/14, matrix			

Exploratory MRI/Imaging Endpoints*				
Change from baseline in joint inflammation a	s measured by dynamic contrast enhanced			
(DCE)-MRI in the most affected hand/wrist:				
 Exchange rate (K^{trans}) 				
 Interstitial volume (V_e) 				
 Plasma volume (V_p) 				
 Initial rate of enhancement (IRE) 				
 Maximal signal intensity enhancement (N 	ИЕ).			
Exploratory Clinical Efficacy Endpoints*				
Change from baseline at all assessment time	epoints for:			
 ACR20/50/70** response rates 				
 Disease activity score for 28 different join 	nts with CRP value (DAS28[CRP]) score			
 DAS28(CRP) remission rates and categories 	prical (European League Against Rheumatism			
[EULAR] good/moderate) response.				
Note: For composite endpoints, e.g. , DAS28(CF	RP), ACR response, etc., each component of			
the assessment will also be reported. Results o	over time, reflecting all assessment time points,			
will also be reported (e.g. , graphically, as well as in Tables and Listings).				
Pharmacokinetic/Target Engagement Endpoints				
 GSK3196165 PK parameters derived from the second sec	he sparse blood samples and using a			
population PK analysis.				
 Pharmacodynamic biomarkers to assess target and a second se	get engagement (IE) (e.g. , serum			
concentration of free GM-USF, GM-USF: GS	K3196165 complex).			
 I o evaluate potential biomarkers of under a set of the set of the	Biomarkers which may be predictive of			
pulmonary alveolar proteinosis (PAP) lung damage (e.g., Krebs von den				
patriogenesis.	Lungen-o [KL-o], serum amyolu A (SAA),			
aciu).				
*Where relevant comparisons will be made between the early and established RA				

*Where relevant, comparisons will be made between the early and established RA subject populations.

** ACR20/50/70: 20%/50%/70% improvement in tender and swollen joint counts and 20%/50%/70% improvement in 3 of the 5 ACR-core set measures.

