4. STUDY DESIGN

4.1. Overall Design

This is a randomized Phase IIa, multi-center, double-blind, placebo-controlled parallel group study to explore the mechanistic evidence that the GM-CSF signaling pathway is active in subjects with RA, and the potential impact of inhibition of this axis by GSK3196165. In addition, the study will assess the potential impact of GSK3196165 on inflammatory structural joint damage in the most affected hand/wrist using MRI.

Approximately 40 subjects with active RA despite treatment with DMARDs (including conventional or biologic) will be randomized into the study, following a screening period

of up to 6 weeks. The total treatment period is up to 10 weeks, with a 12-week follow-up period after the last dose (Week 22). Ideally, 50% of subjects enrolled into the study should have early RA (*e.g.* \leq 2 years since diagnosis). The actual proportion will be monitored throughout the study and randomization may be altered if the projected final proportion with early RA is less than 30%.

A schematic representation of the study design is shown in Figure 1.

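### Does the protocol's uneven wording on early versus established RA leave the stratum results, the cut-off or the status of the question undecided?

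*Protocol*

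**What the plan says.** Four parts of the protocol deal with the stratification factor.

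- **Reporting by stratum.** The synopsis first declares all endpoints exploratory and then says: "They will be summarized for the overall population as well as by RA status". Section 9.4, directly after the paragraph on the repeated-measures Bayesian model for MRI, says: "The data will be analyzed across all subjects, and may also be presented for each disease duration subgroup (stratification factor". A footnote to the table in Section 3 adds: "Where relevant, comparisons will be made between the early and established RA subject populations". Its asterisk is on the exploratory biomarker, imaging and clinical headings, for example "Exploratory MRI/Imaging Endpoints". It is not on the secondary MRI endpoint, which begins "Change from baseline in synovitis, osteitis and erosion as assessed by Outcome Measures in Rheumatology (OMERACT".
- **Cut-off.** The synopsis states: "Randomization will be stratified by early RA (≤2 years since diagnosis) and established RA". It attaches the same limit to the 50% target, and Section 2.1 repeats it. Section 4.1 writes "Ideally, 50% of subjects enrolled into the study should have early RA (*e.g" and then gives the same two-year value. Its next sentence says that "randomization may be altered if the projected final proportion with early RA is less than 30" percent.
- **Status.** The objectives table (in the synopsis and in Section 3) and Section 4.4 include early-versus-established differences in the GM-CSF pathway among the primary or main objectives. The rationale in the synopsis and in Section 2.1 presents the same question as a further, exploratory aim.
- **Inference.** Section 9.1 states that no formal hypothesis is tested. Section 9.4 leaves full details of summaries and analyses to the analysis plan.

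**The concern.** The early-versus-established contrast is the reason for stratifying, so the protocol should say one thing about it. Read separately, the passages could lead two authors to different reports. One working from the synopsis would tabulate every endpoint by stratum. One working from Section 9.4 could leave the tables out and point to the word *may*.

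The footnote in Section 3 does not settle this for the secondary RAMRIS and RAMRIQ endpoints, because they carry no asterisk. For them the synopsis and Section 9.4 are the only statements on stratum reporting.

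The e.g. in Section 4.1 looks worse than it is because of its position. It comes just before the 30% trigger, so it seems to leave open who counts as early RA when the trigger is assessed. If the definition could move, so could stratum membership and the decision to alter randomization. The two descriptions of the question's status seem to add to this: a component of the primary objective is called a mere extra in one place and is optional to present in another.

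**Working it through.** The point is about wording, so most of the check sets passages side by side. The few numbers show its scale.

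**1. The plan's own precision figure.** Section 9.2.1 assumes an SD of 2.5 for MRI synovitis, with 30 active and 10 placebo subjects, and states a 95% half-width of 1.8 points.

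Half-width = 1.96 × 2.5 × √(1/30 + 1/10) = 1.79, or 1.85 with the t quantile on 38 degrees of freedom. Both round to 1.8.

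The figure pools all 40 subjects and does not depend on how the strata are reported. If the 3:1 ratio holds within strata (an assumption), the same normal formula gives:

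| Early RA stratum | Active vs placebo | Half-width |
|---|---|---|
| Half of 40 | 15 vs 5 | 1.96 × 2.5 × √(1/15 + 1/5) = 2.53 |
| 30% of 40 | 9 vs 3 | 1.96 × 2.5 × √(1/9 + 1/3) = 3.27 |

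Stratum results will be descriptive whichever verb governs them.

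**2. How much is in dispute on reporting.** Take the narrow reading, in which the Section 9.4 sentence covers MRI only. The secondary MRI endpoints comprise 2 scoring systems × 3 features (synovitis, osteitis, erosion) × 3 post-baseline scans (Weeks 4, 12 and 22) = 18 endpoint-by-visit results. For these the synopsis says *will* and Section 9.4 says *may*.

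**3. Can both passages be obeyed?**

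| Action | Synopsis | Section 9.4 |
|---|---|---|
| Produce summaries by stratum | complies | complies |
| Omit summaries by stratum | breaches | complies |

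The first row satisfies both passages and the second does not. Permission does not cancel a requirement stated elsewhere in the same document, so all 18 results are owed. There is also a reading with no tension at all. The synopsis speaks of summarizing, while the Section 9.4 sentence speaks of analyzing across all subjects and follows a model paragraph. On that reading descriptive tables by stratum are required, and presenting model output by stratum is optional.

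**4. Is there a second cut-off?** Two years since diagnosis appears twice in the synopsis, once in Section 2.1 and once, after the e.g., in Section 4.1. No other value appears. The sentence that defines the randomization stratum is in the synopsis and has no e.g. The synopsis also sets the 30% trigger right after its own 50% target sentence, where the limit is fixed. The trigger is 0.30 × 40 = 12 subjects, and only one rule is on offer for counting them.

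**5. Does the label do any work?** The primary objective is itself to explore the pathway, and the primary endpoint is change in exploratory biomarkers. The synopsis calls all endpoints exploratory, and Section 9.1 tests no hypothesis. No alpha, test order or sample size depends on whether the question is called main or additional. Appendix 12.9 records that the primary and secondary classes were introduced by Amendment 01 in Sections 1 and 3. The rationale wording is probably a leftover.

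**The case for a change.** The best case for acting is that this is not a detail left to the analysis plan. The protocol addresses stratum reporting twice, with different force, and an analysis plan that omitted the tables could cite Section 9.4 in its defence. The narrow MRI-only reading does not remove the mismatch, because the synopsis sentence covers every endpoint, MRI included. The sections on treatment arms (4.2) and treatment assignment (6.2) do not restate the stratum definition, Section 9.4 calls the factor disease duration, and screening records both disease and symptom duration. A single anchor in the body would therefore be tidy. Aligning the text would be cheap.

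What stands is that *will* and *may* do not match, and that an author who read Section 9.4 alone could go astray. The rest does not carry. The defence for omitting the tables fails once the synopsis is read, and the synopsis is part of the same protocol. The cut-off is anchored to diagnosis wherever it is given, so symptom duration is not a competing definition. Low cost is no reason for a change that alters no analysis, no subject's stratum and no conclusion.

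**Conclusion.** No change to the plan follows. The only true mismatch is one of verbs on stratum reporting. It touches at most 18 MRI endpoint-by-visit results on the narrow reading, and the synopsis already requires all of them. The e.g. in Section 4.1 is best read as a slip for i.e., since no other cut-off is given and the stratum is fixed in the synopsis. The two descriptions of the question's status are compatible in a study whose primary objective is exploratory and which tests nothing.

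The stated half-width of 1.8 points, the 30% trigger (12 of 40 subjects) and the randomization strata are unaffected.

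This conclusion rests on two assumptions: that the synopsis binds as part of the protocol, and that the analysis plan, which is not available here, keeps two years since diagnosis and produces the summaries the synopsis requires.
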